3 THEORETICAL FRAMEWORK

In 2014, the SAGE working group proposed the '3Cs' model of vaccine hesitancy determinants, advancing that complacency, convenience and vaccine confidence explain many of the factors that contribute to vaccine hesitancy. This has been one of the main models of vaccination used in the behavioural literature.

Vaccine **confidence** refers to people not having trust in vaccines and/ or the health system that delivers them. **Complacency** describes situations where people do not consider vaccines to be important. This is likely driven by the fact that the diseases they prevent are not prevalent in many places so people are naive to their potentially devastating effects. Lastly, vaccines might theoretically be available but are not necessarily **convenient** to access. In a separate paper Betsch et al. proposed an additional fourth 'C': **calculation**, to describe individuals who do not receive vaccination because they consider the costs to outweigh the benefits.

The SAGE report also describes vaccine hesitancy as a continuum, with some people accepting some vaccines and refusing others.

More recently, a paper by Brewer et al. proposed the 'Increasing Vaccination Model' to help structure thinking about the behavioural barriers to vaccination (see Figure below). The model suggests that people's attitudes (what they think and feel) and wider social processes jointly influence people's motivations and intentions towards vaccination. Practical barriers then mediate the relationship between favourable intentions to vaccinate and ultimate vaccination behaviour.

Our trial draws on these models in the following ways:

- 1. It aims to change behaviour amongst people who sit along the middle section of the vaccine hesitancy continuum those who might be encouraged to get vaccinated
- 2. The intervention messages relate to different elements of the 'Increasing Vaccination Model' proposed by Brewer et al.. Sending SMS invitations in itself addresses practical issues relating to vaccination (e.g. by making it easier to book an appointment, as recipients can simply click a link within the SMS). The content of the SMS has also been designed specifically to make booking as easy as possible. In addition, different arms in the RCT specifically draw on the three determinants of vaccination behaviour in the model:
 - **Practical barriers:** one of the intervention arms is specifically emphasizing convenience of vaccine appointments available, as this has been identified as a specific practical barrier in the literature;
 - What people think and feel: different messages we aim to test draw on different individual motivations that people might have for vaccination;
 - **Social processes:** in one of the intervention arms we are planning to test a message that highlights positive social norms relating to Covid-19 vaccination.

Recent field trials have shown that reminder text messages about vaccination appointments can improve vaccine uptake by up to $\underline{8-11}\%$ (1.9-4.6pp in absolute terms), and that some messages may be more effective for specific groups. However, it's not clear to what extent the exact wording of these messages would be effective in the UK context given the cultural and linguistic differences between the US and the UK.

The proposed RCT will allow us to determine whether such behaviourally informed **vaccination invitation text messages** could increase UK patients' likelihood of **booking** and **receiving** a coronavirus vaccination.

4 RESEARCH QUESTION/AIM(S)

1. Primary research question: Which BI-informed text messages can increase the likelihood of booking a COVID-19 vaccination appointment and receiving first-dose vaccination, compared to the control text message?

2. Secondary research question: Which BI-informed text messages can increase the likelihood of booking a COVID-19 vaccination appointment and receiving first-dose vaccination **among the following specific subgroups,** compared to the control text message?

- Missing (99)
- Mixed White and any Black (D, E, M, N, P)
- "Other" ethnic group (R, S)
- White any other (C)
- Asian Indian and Mixed White and Asian or other (F, G, H)
- Pakistani, Bangladeshi and other (J, K, L)

Note. The coding and categorisation scheme of the ethnicity groups is adopted from the NIMS system. The number and categorisation of specific subgroups was decided by preliminary power calculation based on expected sample size. A more granular ethnicity breakdown than the one described here would require a larger sample size.

EXTENSION

1. Primary research question: Which BI-informed text messages can increase the likelihood of booking a COVID-19 vaccination appointment and receiving first-dose vaccination, compared to the

control text message?

2. Secondary research question: Can we rule out that BI-informed text messages backfire (decrease by more than 2 percentage points the likelihood of booking a COVID-19 vaccination appointment and receiving first-dose vaccination) **among the following specific subgroups,** compared to the control text message?

- Missing (99)
- Mixed White and any Black (D, E, M, N, P)
- "Other" ethnic group (R, S)
- White any other (C)
- Asian Indian and Mixed White and Asian or other (F, G, H)
- Pakistani, Bangladeshi and other (J, K, L)

Note. See section 8.1 for a more detailed definition of backfire.

4.1 Objectives

Primary Objective:

The primary objective of this study is to identify which BI-informed text messages are effective in increasing the likelihood of booking a COVID-19 vaccination appointment and receiving first-dose vaccination among the younger cohort in England (aged 40~44).

Secondary Objective:

The secondary objective of this study is to examine the primary objective by ethnicity groups.

EXTENSION

Primary Objective:

The primary objective of this study is to identify which BI-informed text messages are effective in increasing the likelihood of booking a COVID-19 vaccination appointment and receiving first-dose vaccination among the individuals in England aged 18~29.

Secondary Objective:

The secondary objective of this study is to rule out a backfire effect of BI-informed messages (compared to control) among ethnic minority groups.

4.2 Outcome

Primary outcome: whether participants book a COVID-19 vaccination appointment (either online or by calling 119) within 72 hours of receiving the SMS invitation. This is a binary outcome, i.e. the booking status will be coded as 1 if the participant makes the booking within the time frame, and coded as 0 if they don't.

Secondary outcome: whether participants receive their first-dose vaccination within 14 days of receiving the SMS invitation. This is also a binary outcome, i.e. the vaccination status will be coded as 1 if participants receive a COVID-19 vaccination within the time frame, and coded as 0 if they don't.

EXTENSION

Primary outcome: whether participants book a COVID-19 vaccination appointment (either online or by calling 119) within 72 hours of being sent the SMS invitation. This is a binary outcome, i.e. the booking status will be coded as 1 if the participant makes the booking within the time frame, and coded as 0 if they don't.

Secondary outcomes:

- whether participants receive their first-dose vaccination within 14 days of being sent the SMS invitation. This is also a binary outcome, i.e. the vaccination status will be coded as 1 if participants receive a COVID-19 vaccination within the time frame, and coded as 0 if they don't.
- whether participants book a COVID-19 vaccination appointment (either online or by calling 119) within 14 days of being sent the SMS invitation. This is a binary outcome, i.e. the booking status will be coded as 1 if the participant makes the booking within the time frame, and coded as 0 if they don't.

5 STUDY DESIGN AND METHODS of DATA COLLECTION AND DATA ANALYSIS

5.1 Study design

This is an 8-arm field RCT with randomisation at individual level.

- **Control group** will receive the business-as-usual SMS invitation.
- **Treatment groups** will receive a behaviourally-informed (BI) SMS vaccination invitation, and the content of the messages will cover several evidence-based BI concepts. (All groups Treatment and Control will also receive the BAU letter invitation).
- **Spillover effects.** In individual randomisation trials, we typically consider spillover risks to be low. However, given that the trial will target the universe of eligible NHS patients, the chance of two people in the same household receiving different messages is not negligible. Our stance is that i) even if spillover happens, it will shrink the between-arm difference, thus we will only under-estimate rather than over-estimate the treatment effects; ii) implementation risks in running this trial as a clustered RCT (household level) exceed the risks of running this trial with individual randomisation. The NHSEI communications team have also drafted copy to address potential issues if people were to question the authenticity of the NHS SMS invitations on social media.

EXTENSION

This is a 7-arm field RCT with randomisation at individual level.

- Control group will receive the control SMS invitation (same message as in the main trial).
- **Treatment groups** will receive a behaviourally-informed (BI) SMS vaccination invitation, and the content of the messages will cover several evidence-based BI concepts. (All groups Treatment and Control will also receive the BAU letter invitation).

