7.2 Sampling

7.2.1 Size of sample

Estimated size of the 40 - 49 years old cohort (data source: NIMS):

- 5.44 million in total
- 544,000 per year group

Expected **sample size** for this study:

- We expect to send the SMS invitations to 3 year groups (42, 43, 44), i.e. 1.63 million participants in total
- The actual sample size will depend on vaccine supply and vaccination capacity

EXTENSION

Estimated size of the 18 - 29 years old cohort (data source: NIMS):

- 8 million in total
- 670,000 per year group

Expected **sample size** for this study:

- We expect to send the SMS invitations to 4 year groups (26, 27, 28, 29), i.e. 2.88 million participants in total
- The actual sample size will depend on vaccine supply and vaccination capacity

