8.1 Assessment and management of risk

One risk is that the behaviourally-informed messages have an unintended **backfire effect** and reduce vaccination uptake in some groups. This risk has been minimised by developing the messages based on the evidence available from related research, as well as input from experts at the Behavioural Insights Team (BIT), NHS England and NHS Improvement (NHSEI), and Public Health England (PHE). To further mitigate this risk, messages have been pre-tested with an online panel and messages leading to a significant decrease in intention to get vaccinated have not been included in the trial. In addition, all participants who haven't booked an appointment within two weeks will receive a reminder delivered via post, further mitigating the risk of potential message backfiring.

Mitigation strategies:

If backfire occurs for any BI message or for any ethnicity group, we propose the following mitigation strategy: **every participant** who hasn't booked an appointment will be sent the default reminder letter in **14-16 days** (the status quo being 14-21 days) after they receive the SMS invitation.

Definition of backfire: Any BI message arm whose corresponding booking rate within 72 hours is equal to or more than **2** percentage points lower (and the effect is **significant**) compared to the business-as-usual message (either for all sample or for any of the 6 specific ethnic groups). It's worth noting that if the negative effects are *not statistically significant*, or if the magnitude of negative effects is *less than 2 percentage points*, we won't classify them as backfire.

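### Household spillover that shrinks differences is conservative for showing benefit but anti-conservative for ruling out backfire, and the protocol states only the first

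*Protocol*

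**What the plan says.** Section 5.1 acknowledges that, because the trial covers all eligible patients, "the chance of two people in the same household receiving different messages is not negligible". It then argues that if spillover occurs "it will shrink the between-arm difference", so that "we will only under-estimate rather than over-estimate the treatment effects". A second, separate argument follows: randomising by household would carry greater implementation risk.

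The extension changes the secondary question. Section 4.1 makes it the aim to "rule out a backfire effect of BI-informed messages (compared to control) among ethnic minority groups", and section 4 defines backfire as a message that would "decrease by more than 2 percentage points the likelihood of booking a COVID-19 vaccination appointment" and of receiving the first dose. Section 8.1 has an operational rule, which covers the whole sample and each of six ethnic groups. It begins "Any BI message arm whose corresponding booking rate within 72 hours is equal to or more than" and continues with a 2-point shortfall against the business-as-usual message that must also be statistically significant. Smaller or non-significant falls are not classed as backfire.

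The extension text in section 5.1 does not return to spillover, and the amendment history says that methods carry over from the first experiment.

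**The concern.** Bias toward zero is reassuring only when the conclusion sought is that a difference exists. The extension's secondary objective seeks the opposite: that a harmful difference of a given size does not exist. Dilution then helps the sponsor reach the favourable conclusion. The same holds for the section 8.1 rule in both parts of the study, since an attenuated harm is less likely to reach the observed 2-point threshold that triggers the planned mitigation.

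At stake is how far a no-backfire statement about ethnic minority groups can be trusted. A reader who relies on section 5.1 as written would take spillover to be a safe bias throughout and would apply no caution to that statement.

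**Working it through.** **Inputs from the protocol.** Margin: 2 percentage points (sections 4 and 8.1). Extension size: 2.88 million over 7 arms (sections 7.2.1 and 5.1), so 2,880,000 / 7 = about 411,400 per arm.

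**Inputs assumed, because the protocol gives none.** Attenuation c, the share of the contrast lost through message-sharing: 10%, 20%, 30%. Ethnic subgroup: 5% of an arm, so n = 0.05 × 411,400 = about 20,600. Control booking rate p: 40%. Intervals and tests are unadjusted, two-sided 5%. The protocol states no spillover figure, so there is nothing of its own to reproduce.

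**Step 1, dilution.** Observed difference d = (1 − c) × true difference. A true −2.5 becomes −2.25, −2.00 and −1.75 points. The attenuation that brings a true fall down to the 2-point threshold is 1 − 2/|true|: 20% for a true fall of 2.5 points and 33% for 3.0.

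**Step 2, precision.** SE = √{[p(1 − p) + (p + d)(1 − p − d)] / n}. With p = 0.40 and d = −0.025: √[(0.2400 + 0.2344) / 20,571] = 0.0048, or 0.48 point.

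**Step 3, chance of meeting the section 8.1 rule.** Significance needs a fall of about 1.96 × 0.48 = 0.94 point, so the 2-point threshold is the binding condition. The chance is Φ[(−2 − d) / SE]. For a true −2.5 without dilution: 0.50 / 0.48 = 1.04, giving 85%. At 10%: 0.25 / 0.48 = 0.52, giving 70%.

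**Step 4, chance that a 95% interval wrongly excludes a 2-point fall when the true fall is exactly 2.0.** The chance is Φ[(d + 2) / SE − 1.96]. At 10%, d = −1.8: 0.20 / 0.48 − 1.96 = −1.54, giving 6.1%.

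| Attenuation c | True −2.5 appears as | Chance rule is met | True −2.0 appears as | Chance interval wrongly excludes −2 |
|---|---|---|---|---|
| 0 | −2.50 | 85% | −2.0 | 2.5% |
| 10% | −2.25 | 70% | −1.8 | 6.1% |
| 20% | −2.00 | 50% | −1.6 | 12.9% |
| 30% | −1.75 | 30% | −1.4 | 23.8% |

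**Range over other assumed inputs.** I varied the subgroup from 2% to 10% of an arm and booking from 20% to 40%.

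- True −2.5: the chance of meeting the rule is 75% to 97% without dilution and 18% to 37% at c = 30%. It is 50% throughout at c = 20%.
- True −2.0: the chance of wrong exclusion is 4.5% to 10.9% at c = 10% and 12.1% to 58.7% at c = 30%.

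The drop is steepest in the larger, more precisely estimated groups, because more data do not remove a bias.

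**The case against.** **The sentence in section 5.1 is not false.** Under dilution a negative effect is also under-estimated in size, so the words remain literally true of household message-sharing. This stands. The fault is that their consequence for the harm objective is left unstated. For the primary question of benefit, the reasoning is sound.

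**The dilution may be small.** It needs two participants in one household, in different arms, influencing each other before booking, within the few year groups invited in stages. This also stands, and the protocol supports no particular value of c. But it is the protocol itself that calls the mixing non-negligible, and the planned extract contains no addresses or locations from which c could be estimated.

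**Sampling error in the subgroups is larger than the bias.** On the central assumptions the 95% half-width is about 0.94 point, against a shift of 0.2 to 0.6 point for a true −2.0 at c = 10% to 30%. A reader might take the very high precision of the whole sample to mean that bias alone settles the conclusion. The documents do not support that, because the objective concerns ethnic subgroups. There the bias shifts the error rates, as tabulated.

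**A reader might also infer that arms compete for scarce appointments, so that between-arm differences are inflated.** The documents do not support this either. Section 7.2.1 says "The actual sample size will depend on vaccine supply and vaccination capacity", which ties capacity to the number invited and does not report a shortage of slots within 72 hours. The protocol's parameter is the contrast with the control message, and nowhere does it present that contrast as the gain from sending one message to everyone. In an illustrative simulation (30% against 32% wanting to book), proportional rationing with slots for 80% of demand reduced the arm difference from 1.86 to 1.50 points. Inflation above the unconstrained difference appeared only when arms were also assumed to book at different speeds.

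**Sensitivity analyses usually belong in the SAP, which is not at hand.** This is true of the added calculation. It does not excuse the protocol's general statement, which is what a reader will rely on.

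**Conclusion.** The point holds in a limited form. Section 5.1 gives half of the consequence of household dilution. The missing half bears on the extension's secondary objective and on the backfire rule in section 8.1.

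The direction follows from the protocol's own mechanism and objective and needs no outside figure. The size rests on assumed attenuation, subgroup share and booking rate: modest at 10%, material at 20% to 30%.

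Nothing here argues against individual randomisation, which section 5.1 also defends on implementation grounds, or against the primary analysis.

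**What to change.** 1. In section 5.1, limit the statement on under-estimation to claims of benefit under household message-sharing. Add that the same dilution weakens any conclusion that backfire has been ruled out.

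2. Beside the planned backfire assessment, and without replacing its rule, add a sensitivity result for each message and ethnic group. Take the lower 95% limit L of the difference in booking rates, in percentage points, and report the attenuation c at which L / (1 − c) reaches −2, that is c = 1 − |L|/2 for L between −2 and 0. For example, L = −1.9 gives c = 5%, so the conclusion is fragile; L = −1.0 gives c = 50%, so it is robust. If L is already below −2, a 2-point fall is not excluded even without dilution. If L is zero or above, no attenuation overturns the conclusion.

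3. Word each no-backfire conclusion to match, naming the attenuation up to which it holds.

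The cost is a wording change and one line of arithmetic per comparison, with no new data and no change to randomisation or the model. The price is a slightly weaker no-backfire claim where the limit lies close to the margin.

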5.2 Data collection

We will collect three types of data: 1) a pseudonymised identifier, i.e. a unique identifier linked to a patient's NHS number as well as information on which version of the SMS invitation received; 2) demographic profile, including age, gender, and ethnicity; 3) outcome-related data, including vaccine booking rate within 72 hours of receiving the text message invitation and vaccination status within 14 days of receiving the text message. We will **NOT** receive data such as participants' names, addresses, GP practice, location, phone numbers or any information on medical conditions. The table below illustrates what a dummy final data set looks like.

Pseudonymised randomly generated number to merge data						Note. T analysi	his data set s by BIT and	will be received for NHSEI researchers	
extracts	tracts Randomisation Variables to construct primary outcomes					Personal characteristics			
Pseudony- mised identifier	Message	Timestamp first message sent	Timestamp appointment booked	First appointment date	Received first-dose vaccine	Ag	e	Gender	Ethnicity
1234XXX	A	23/03/21 10.00	23/03/21	30/03/21	Y	49		М	African
4678XXX	В	23/03/21 10.00	23/03/21	31/03/21	Y	48		М	White and Black Caribbean
9101XXX	С	23/03/21 10.00	24/03/21	30/03/21	N	48		F	Pakistani or British Pakistani
1213XXX	D	23/03/21 10.00	NA (not booked)	NA	NA	49		М	British, Mixed British
11617XXX	E	23/03/21 10.00	24/03/21	1/04/21	N	47		М	Any other White background
1617XXX	A	23/03/21 10.00	NA (not booked)	NA	Y	48		F	Bangladeshi or British Bangladeshi
1367XXX	В	23/03/21 11.00	NA (not booked)	NA	N	47		F	Caribbean

5.3 Data analysis Primary analysis

The trial will be analysed as intention-to-treat (message sent rather than message read). In order to estimate the impact of different SMS invites on vaccine booking and vaccination rate, we will use the following logistic model:

```
Outcome_i \sim bernoulli(p_i);
logit(p_i) = \alpha + \beta_1 BImessage1 + \beta_2 BImessage2_i + ... + \beta_7 BImessage7_i + \gamma X'
where:
```

- Outcome_i refers to:
 - Any booking made within 72 hours of sending the message (*primary outcome, ITT*).
 The booking status outcome will be coded as 1 if participants make the booking within the time frame, and coded as 0 if they don't.
 - Any first-dose vaccination received within 14 days of receiving the SMS (*secondary outcome*). The vaccination status will be coded as 1 if participants receive their vaccination within the time frame, and coded as 0 if they don't.
- BImessage_1...BImessage_7 is a set of dummies, each representing one of the 7 behaviorally inform messages drafted. The reference group is the group receiving the control message this is why there are 7 dummies instead of 8
- X' is a vector of characteristics such as age, gender and ethnicity subgroups (the reference group will be White British and Irish (A, B), and the other subgroups are specified in the research question section slide). It also includes timestamps e.g. date and time of receiving the text.

 $\hat{\beta}_1...\hat{\beta}_7$ constitute the estimated parameter of interest. They represent the impact of BImessageX on the outcome, compared to the control sms.

P-values will be adjusted for multiple comparisons using Benjamini-Hochberg correction, treating each ethnicity as a separate family of hypothesis tests in which each arm is compared to the control with a maximum false discovery rate of 5%.

Secondary analysis

In order to estimate the impact of different SMS invites on vaccine booking and vaccination rate **among each ethnic group**, we will use the following logistic model:

 $Outcome_i \sim bernoulli(p_i);$ $logit(p_i) = \alpha + \beta_1 BImessage1 + \beta_2 BImessage2_i + ... + \beta_7 BImessage7_i + \gamma X' if ethnic group = k$ where:

- Outcome_i refers to:
 - Any booking made within 72 hours of sending the message (*primary outcome, ITT*).
 The booking status outcome will be coded as 1 if participants make the booking within the time frame, and coded as 0 if they don't.
 - Any first-dose vaccination received within 14 days of receiving the SMS (*secondary outcome*). The vaccination status will be coded as 1 if participants receive their

vaccination within the time frame, and coded as 0 if they don't.

- X' is a vector of characteristics such as age, gender. It also includes timestamps e.g. date and time of receiving the text.
- k=1...7 are the different ethnicity subgroups. The **reference group** will be White British and Irish (A, B), and **the other subgroups** 1...6 are specified in the research question section slide).

 $\hat{\beta}_1 \dots \hat{\beta}_7$ constitute the estimated parameter of interest. In each regression, they represent the impact of BImessageX on the outcome, compared to the control SMS, for the ethnic group k considered.

P-values will be adjusted by multiple comparisons using Benjamini-Hochberg correction, treating each ethnicity as a separate family of hypothesis tests in which each arm is compared to the control with a maximum false discovery rate of 5%.

EXTENSION

The analysis will follow the same strategy of the main experiment, but it will include one additional secondary outcome - booking rate within 14 days from being sent the message.

Statistical packages

Researchers at BIT will use Rstudio1.2 & R3.6.0 and Stata 16th Edition statistical packages to analyze the results.

